5.1.2 Sample size

When comparing the peak GM immunogenicity outcomes of children with that of adults, or between vaccine types, a sample size of 61 in each group would assure that a two-sided test with $\alpha=0.05$ has 99% power to detect an effect size with a Cohen's d value=0.78, corresponding to 1.67-fold difference on the linear scale, or 0.51 after natural log transformation, between 2 groups and a standard deviation (SD) of 0.65 on the natural log scale within each group. For assays with higher technical requirements such as PRNT, 66 evaluable adolescents/children and 16 evaluable adults tested would achieve 80% power to detect the same non-inferiority margin with the same α and SD; lower sample sizes may be applied on practical grounds. The statistical assumptions on effect size referred to the trial design and results by French et al in NEJM (2021) which found a GMR of 1.76 (95% CI 1.47-2.10) for PRNT50 in adolescents to young adults after 2 doses of BNT162b2. For the proportion of participants with a positive result in immunogenicity outcomes or ARs, 110 adolescents would yield a 95% chance to detect the true value within 7.5% of the measured percentage, assuming a prevalence of 80%. Recruitment of 120 participants were targeted per vaccine regimen and age group to accommodate for attrition.

Reference: French RW et al. Safety, Immunogenicity, and Efficacy of the BNT162b2 Covid-19 Vaccine in Adolescents. N Engl J Med (2021); 385:239-250.

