5.1 Hypotheses and decision rules

5.1.1 Immunogenicity hypothesis

A primary objective of the study is to prove or disprove the hypothesis that immunogenicity of either vaccines are non-inferior in healthy adolescents/children to that in healthy adults at the acute dose 2 timepoint (around 1 month post-dose 2). We test the hypothesis in two-dose and three-dose healthy evaluable immunogenicity populations for each of the following specified tests.

$$H_0: \ln(\mu_2) - \ln(\mu_1) < \ln(0.6)$$

$\ln(0.6)$ refers to a non-inferiority margin of 1.67 fold, while $\ln(\mu_2)$ and $\ln(\mu_1)$ refer to the natural log of the geometric mean of the following immunogenicity assessments performed at the acute dose 2 timepoint from recipients of respective vaccines aged between 5-10 or 11-17 years and 18 or above. If the lower limit of the 95% confidence interval for mean ratio is ≥ 0.6 , the respective non-inferiority objective is met.

1. Anti-S binding antibody level
2. Anti-S-RBD binding antibody level
3. Surrogate neutralizing antibody inhibition level
4. Neutralizing antibody titer
5. Anti-S antibody avidity index
6. Anti-S FcgRIIIa-binding antibody level
7. Total responsive Th1 (to S, and N and M if applicable)
8. Total responsive Tc1 (to S, and N and M if applicable)
9. Anti-N binding antibody level
10. Anti-N-CTD binding antibody level

In addition, we also test a hypothesis that immunogenicity of a single dose of BNT162b2 in adolescents is non-inferior to that of two doses of BNT162b2 in adults.

For healthy children and adolescents receiving intradermal vaccination, we test also a second hypothesis that superior immunogenicity outcomes can be detected in intradermal route over intramuscular route in participants of the same age group, as well as for non-inferiority.

$$H_0: \ln(\mu_2) - \ln(\mu_1) \leq \ln(1)$$

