7.2 Interim analysis 2 (Jan 2022)

Interim analysis will be performed in Jan 2022 when 100 healthy participants have completed post-dose 2 assessment under the age of 18 years, including at least 50 for PRNT, for each vaccine.

While paediatric patients with prior COVID-19 and severe paediatric/immune conditions have been enrolled in this trial, the analysis of these participants will be separate. Safety, reactogenicity and immunogenicity analyses will focus on healthy participants.

Key objectives of this analysis are to describe the reactogenicity and safety of these vaccines in the pediatric age group, compare the acute immunogenicity of the vaccines in adolescents and adults, and compare the acute immunogenicity of the two vaccines in adolescents. We aim to demonstrate non-inferiority in a range of immunogenicity endpoints in adolescents to adults.

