7.3 Interim analysis 3 (May 2022)

Interim analysis will be performed in May 2022 when more than 60 healthy adolescents receiving CoronaVac and 60 receiving BNT162b2 have completed post-dose 3 assessment under the age of 18 years, including at least 20 for PRNT for each vaccine. Reactogenicity and safety will be analyzed. Antibody and T cell responses against Omicron will also be evaluated.

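### The PRNT power of 80% is stated correctly, but 16 adults limit it: the same 82 assays split 50:32 give about 93% at a true GMR of 1, and section 7.2 fixes no adult number

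*SAP*

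**What the plan says.** SAP section 5.1.1 lists the neutralizing antibody titer among its non-inferiority tests of children or adolescents against adults, separately for each vaccine. The objective is met as follows: "If the lower limit of the 95% confidence interval for mean ratio is ≥ 0.6".

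Section 5.1.2 sets 61 per group for 99% power in general. For technically demanding assays such as PRNT it uses smaller, unequal groups: "66 evaluable adolescents/children and 16 evaluable adults tested would achieve 80% power", with the same margin, alpha and SD. It then adds that "lower sample sizes may be applied on practical grounds", and names no minimum. On recruitment it says: "Recruitment of 120 participants were targeted per vaccine regimen and age group to accommodate for attrition". It gives no reason for the roughly 4:1 split of PRNT assays.

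Section 7.2 describes the January 2022 interim analysis, whose stated aims include showing non-inferiority of adolescents to adults. It is triggered by 100 healthy under-18s completing the post-dose 2 assessment, "including at least 50 for PRNT, for each vaccine". No adult PRNT number appears there.

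**The concern.** When the number of assays is the limit, a two-group comparison of means with equal SDs is most precise when the groups are close to equal. A 66:16 split spends most of the assays where they add least. The adult group could apparently be larger, since 120 are targeted per regimen and age group.

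The 80% is also not protected where it is used. It rests on 66 adolescents/children, the analysis in 7.2 can start with 50, and 5.1.2 allows lower numbers without a floor.

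Neutralizing titer is a primary endpoint (3.1.2.3). What is at stake is an avoidable chance of failing to show non-inferiority that is truly present, for an assay whose group sizes the plan can choose.

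**Working it through.** **Inputs, all from the SAP**
- Margin: 0.6, so the distance from a true GMR of 1 to the margin is |ln 0.6| = 0.511 (5.1.1; 5.1.2 rounds this to 0.51).
- SD 0.65 on the natural log scale in each group (5.1.2).
- Two-sided alpha 0.05, which is 0.025 for the lower confidence limit (5.1.1, 5.1.2).
- True GMR of 1. The SAP does not say this, but it is implied by powering on the full margin.
- Adults at the 7.2 analysis: **an assumption**. 16 is the only adult PRNT number in the SAP.

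**Method.** SE = 0.65 × √(1/n₁ + 1/n₂). The noncentrality parameter is 0.511/SE. Power is the probability that a noncentral t variable with n₁ + n₂ − 2 degrees of freedom exceeds the 97.5% point of the t distribution.

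**Step 1: reproduce the plan's figures.**
- 61:61 gives 99.0%, as stated.
- 66:16: √(1/66 + 1/16) = 0.279, SE = 0.181, noncentrality 0.511/0.181 = 2.82, power 79.6% (80.5% by normal approximation). The stated 80% is correct.

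**Step 2: find what limits it.** With 16 adults, the term 1/16 = 0.0625 dominates 1/66 = 0.0152. Raising adolescents from 66 to all 120 targeted gives √(1/120 + 1/16) = 0.266 and power of only 83%.

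**Step 3: reallocate the same 82 assays, and vary the adults at the 7.2 minimum (true GMR 1, SD 0.65).**

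| Adolescents : adults | Assays | √(1/n₁ + 1/n₂) | Power |
|---|---|---|---|
| 66 : 16 (5.1.2) | 82 | 0.279 | 79.6% |
| 50 : 32 | 82 | 0.226 | 92.9% |
| 50 : 16 (7.2 minimum, 16 adults assumed) | 66 | 0.287 | 76.9% |
| 50 : 18 | 68 | 0.275 | 80.4% |

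With 50 adolescents, power runs from 67% at 12 adults through 88% at 24 to 98% at 61. The number that 7.2 omits is therefore the one that matters most.

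**Step 4: vary the assumptions.**

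| True GMR, SD | 66:16 | 50:16 | 50:32 |
|---|---|---|---|
| 0.9, 0.65 | 60% | 57% | 78% |
| 1.0, 0.65 | 80% | 77% | 93% |
| 1.2, 0.65 | 97% | 96% | 99.7% |
| 1.76, 0.65 | about 100% | about 100% | about 100% |
| 1.0, 0.80 | 62% | 59% | 80% |

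**Step 5: what the adolescent side loses.** The SE of the adolescent ln geometric mean titre is 0.65/√66 = 0.080 at 66 and 0.65/√50 = 0.092 at 50. For the comparison of the two vaccines in adolescents, at the same 1.67-fold difference, power is 99.4% at 66:66 and 97.3% at 50:50.

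**The case against.** The strongest reply is that nothing here is miscalculated. Eighty percent is a conventional target, the arithmetic is right, and the floor proposed below is itself 80%. That stands: this is a question of efficiency, not an error.

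The reply has further force on these points:
- **The gain depends on the true GMR.** Section 5.1.2 cites a GMR of 1.76 for PRNT50 after two doses of BNT162b2, and there every split has near-certain power. This stands for that vaccine in adolescents. It does not settle CoronaVac or ages 5-10, which 5.1.1 also tests, and the SAP's own calculation takes no credit for 1.76.
- **The 77% is not a document figure.** It borrows 16 adults from 5.1.2, and 50 is a minimum that triggers the analysis, not a cap. On that assumption, the drop from 66 to 50 adolescents costs under 3 points.
- **Adolescent titres serve other purposes.** The efficacy prediction in 6.2.2 uses them, and moving assays to adults makes it slightly less precise. This is a real cost, though a small one.
- **Adult samples are targeted, not guaranteed.** The SAP does not say that adult sera are already collected or stored, and section 4.2 restricts who is evaluable. That assay count is the binding limit is itself inferred from the wording on technical requirements and practical grounds.

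A reader might also infer that the post-dose 3 analysis in 7.3, "including at least 20 for PRNT for each vaccine", runs a badly underpowered non-inferiority test. The SAP does not support this. Section 7.3 gives no adult number and states no such test. Section 5.1.1 does name the three-dose population, but it places the hypothesis at the acute dose 2 timepoint, and 6.1.2.7 ties non-inferiority to one month after dose 2.

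**Conclusion.** The point holds as a cheap improvement. Section 5.1.2 states its 80% correctly, but the same 82 assays split 50:32 would give about 93% at a true GMR of 1 and SD 0.65. That cuts the chance of missing true non-inferiority from about 20% to about 7% under those assumptions. At a true GMR of 0.9 the comparison is 60% against 78%; at 1.76 there is no material difference.

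Separately, the 66 in 5.1.2, the minimum of 50 in 7.2, the absent adult number in 7.2 and the open permission to go lower leave the 80% unsecured at the analysis that needs it. The size of that gap cannot be fixed from the SAP; it is about 3 points if 16 adults are tested. It would be wrong to conclude that the sample size is miscalculated, or that the plan necessarily accepts a 20-23% failure risk whatever the true ratio.

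**What to change.** 1. In section 5.1.2, plan PRNT on 50 evaluable adolescents and 32 evaluable adults per vaccine, provided that enough evaluable adult samples are available from the 120 targeted. State that the resulting 93% assumes a true GMR of 1 and SD 0.65.
2. Replace the sentence "lower sample sizes may be applied on practical grounds" with a floor of 50 adolescents and 18 adults, which keeps 80%.
3. Carry the same adolescent and adult numbers into section 7.2.

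**Cost.** The assay total stays at 82. The adolescent minimum of 50 in 7.2 is kept. Adolescent precision falls slightly (SE of ln geometric mean titre 0.092 instead of 0.080), which slightly widens the efficacy prediction, and power for the between-vaccine PRNT comparison falls from 99% to 97%. If 32 evaluable adults cannot be found for a vaccine, test as many as there are, not fewer than 18, and report the power that goes with that number.

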5.1.3 Multiplicity consideration

Not considered.

5.2 General methods

Confidence intervals for all endpoints will be 95% (2-sided) unless otherwise noted.

5.2.1 Categorical variables

We describe categorical variables with percentages, numerator (n) and denominator (N), and 95% CI using the Clopper-Pearson method. For differences in binary data between groups, 95% CI will be derived from Fisher exact test.

5.2.2 Continuous variables

We describe continuous variables with case number (n), mean, median, standard deviation, minimum and maximum values.

5.2.2.1 Geometric means

Geometric means and the corresponding 95% CI will be calculated for some immunogenicity outcomes, including neutralizing antibody titers and responsive T cell frequencies.

5.2.2.2 Geometric mean fold rises/changes

Geometric means of a later time point may be divided by that of an earlier time point, and limited to participants with non-missing values at both timepoints.

5.2.2.3 Geometric mean ratios

Geometric mean ratio will be calculated to compare some immunogenicity outcomes between two groups.

5.2.2.4 Geometric mean fold rise ratios

Geometric mean fold rise ratio will be calculated to compare fold change of some immunogenicity outcomes between two groups at two time points.

6 Analysis and summary

6.1 Primary analysis

6.1.1 Reactogenicity endpoints

6.1.1.1 Adverse reactions

To satisfy the primary objective of describing the reactogenicity, we analyze reactogenicity data based on the following:

- Estimand: Percentage of participants reporting a particular solicited reaction by maximum severity, in total for all grades
- Analysis set: (healthy) safety population
- Time-point: after each dose on days 0-7
- Statistics: percentage (and 2-sided Clopper-Pearson 95% CI), n and N; each reaction (total) compared across vaccines by Fisher's exact test
- Figure: stacked bar chart showing percentage of participants reporting a particular reaction by maximum severity in each age category and vaccine type

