2.1 Study Objectives

Primary objectives

1. Report the frequencies of reactogenicity within the 7 days after each vaccine injection;
2. Compare frequencies of reactions among the vaccines;
3. Report the short-term and long-term (up to 36 months post-vaccination) immunogenicity outcomes including spike protein IgG and related markers, neutralizing antibody titres and B and T cell immune responses;
4. Compare immunogenicity outcomes between children and adults, such that the geometric mean values of immunological parameters are statistically non-inferior (0.6 of adult value) in children, and differences between vaccines in children

Secondary objectives

5. Describe adverse events and serious adverse events during the study period;
6. Explore any parameters or markers predictive and correlative of immune responses to vaccination;
7. Short-term and long-term (up to 36 months post-vaccination) longitudinal differences in non-spike protein antibody titres for participants receiving CoronaVac;
8. Short-term and long-term (up to 36 months post-vaccination) longitudinal differences in type I and II T cell immune responses between vaccines and between children and adults
9. Differences in short-term and long-term (up to 36 months post-vaccination) longitudinal differences in spike protein IgG and related markers, neutralizing antibody titres and cellular immune responses against emerging viral variants between vaccines, and between children and adults;
10. Vaccine breakthroughs as documented by N and ORF8 antibodies in subjects receiving BNT162b2, or ORF8 in subjects receiving CoronaVac, with estimation of potential immunological correlates of protection against infection.
11. Explore the psychosocial impact of COVID-19 vaccination in adolescents
12. Impact of pre-existing conditions on safety, reactogenicity and immunogenicity of vaccines
13. Impact of vaccination on adolescents with previous COVID-19 and long COVID

14. Short-term and long-term (up to 36 months post-vaccination) longitudinal differences in SARS-CoV2 whole blood immune responses between vaccines and between children and adults
15. Short-term and long-term (up to 36 months post-vaccination) longitudinal differences in SARS-CoV2 nasopharyngeal immune responses between vaccines and between children and adults
16. Predict vaccine efficacy based on established immune correlates of protection

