4.3 Reactogenicity and safety populations

Population	Description
Healthy safety	
All eligible participants who
 
 ● generally healthy without any major immunocompromise ● received at least one dose of the vaccine ● has proven seronegative or unknown at baseline and not known to be infected ● reported any safety or reactogenicity data
All safety	
All eligible participants who
 
 ● received at least one dose of the vaccine ● reported any safety or reactogenicity data

5 Methodology and hypotheses

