6.1.2.9 GMR of S and S-RBD binding IgG, surrogate neutralizing antibody inhibition level, and neutralizing antibody titers, IgG avidity index and FcγRIIIa-binding IgG in participants 11-17 years of age receiving 2 doses of BNT162b2 to those receiving 2/3 doses of CoronaVac

- Estimands: geometric mean ratio
- Analysis set: 2/3-dose evaluable and expanded immunogenicity populations
- Time points: 1 month after dose 2, 2 weeks after dose 3, 6, 18 and 36 months after vaccination; including cross-comparison of two doses of BNT162b2 and three doses of CoronaVac
- Statistics: exponentiated difference in mean and CI95 on natural log scale for geometric means and two-sided CI95 (or one-sided CI97.5).
- Figure: forest plot
- Intercurrent events: Values below the cut-off/lower limit of detection/quantification may be set to 0.5 of the cut-off/limit for analysis if applicable for the assay.

6.1.2.10 GMR of total S responsive Th1 and Tc1 cell frequencies in participants 11-17 years of age receiving 2 doses of BNT162b2 to those receiving 2/3 doses of CoronaVac

- Estimands: geometric mean ratio
- Analysis set: 2/3-dose evaluable and expanded immunogenicity populations
- Time points: 1 month after dose 2, 2 weeks after dose 3, 6, 18 and 36 months after vaccination; including cross-comparison of two doses of BNT162b2 and three doses of CoronaVac

- Statistics: exponentiated difference in mean and CI95 on natural log scale for geometric means and two-sided CI95 (or one-sided CI97.5).
- Figure: forest plot
- Intercurrent events: Values below the cut-off/lower limit of detection/quantification may be set to 0.5 of the cut-off/limit for analysis if applicable for the assay.

6.1.2.11 GMR of S and S-RBD binding IgG, surrogate neutralizing antibody inhibition level, and neutralizing antibody titers, IgG avidity index and FcgRIIIa-binding IgG in participants receiving intradermal CoronaVac to intramuscular CoronaVac

- Estimands: geometric mean ratio
- Analysis set: 2/3-dose evaluable and expanded immunogenicity populations
- Time points: 1 month after dose 2, pre-dose 3, 2 weeks after dose 3, 6, 18 and 36 months after vaccination
- Statistics: exponentiated difference in mean and CI95 on natural log scale for geometric means and two-sided CI95 (or one-sided CI97.5).
- Figure: forest plot
- Intercurrent events: Values below the cut-off/lower limit of detection/quantification may be set to 0.5 of the cut-off/limit for analysis if applicable for the assay.

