6.3 Subgroup analysis

As described elsewhere in this protocol, subgroup analyses include:

- age (18 years and above, 11-17 years, 3-10 years, and below 3)
- healthy history, conditions include:
 - Immune diseases
 - Combined defects
 - Humoral defects
 - Immune dysregulation
 - Innate defects
 - Phagocytic defects
 - Renal disorders
 - On immunosuppression only
 - On dialysis
 - Post-kidney transplant
 - Hematological conditions
 - Post-HSCT
 - Acute lymphoblastic leukemia
 - Allergy
 - To PEG-containing drugs
 - To first dose of COVID-19 vaccine
 - Neuromuscular disorders
 - Immune-mediated
 - Muscular dystrophy on immunosuppression
 - Prior COVID-19

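### Reactogenicity and adverse events are not broken down by injection route, although intradermal and intramuscular CoronaVac are compared for immunogenicity

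*SAP*

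**What the plan says.** Section 2.1 makes reporting of reactogenicity in the week after each injection primary objective 1. Primary objective 2 is: "Compare frequencies of reactions among the vaccines".

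Section 6.1.1.1 carries these out. Its figure is a "stacked bar chart showing percentage of participants reporting a particular reaction by maximum severity in each age category and vaccine type", and its statistics line has "each reaction (total) compared across vaccines by Fisher's exact test". Results are given after each dose and by maximum severity.

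Both safety populations in section 4.3 admit anyone who "received at least one dose of the vaccine" and reported data; the healthy set adds health and infection criteria. Neither is split or restricted by route. Section 6.2.1 (unsolicited events) names no comparison groups. The subgroup list in 6.3 opens with "age (18 years and above, 11-17 years, 3-10 years, and below 3" and continues with health conditions only.

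Route does appear for immunogenicity. Section 5.1.1 states: "For healthy children and adolescents receiving intradermal vaccination, we test also a second hypothesis". That hypothesis is that "superior immunogenicity outcomes can be detected in intradermal route over intramuscular route in participants of the same age group", and non-inferiority is tested as well. Section 6.1.2.11 gives antibody geometric mean ratios for "participants receiving intradermal CoronaVac to intramuscular CoronaVac", and 6.1.2.12 does the same for T cells at 11-17 years.

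**The concern.** Intradermal CoronaVac is studied as an intervention with its own hypothesis. If the reactogenicity analysis is programmed from 6.1.1.1 and 4.3 alone, there is one CoronaVac group per age category. Two things follow.

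- **Primary objective 1.** A claim of superior intradermal immunogenicity could be reported with no reactogenicity or adverse-event result for that route beside it.
- **Primary objective 2.** The comparison of BNT162b2 with CoronaVac would depend on what share of CoronaVac recipients received it intradermally. The SAP neither fixes nor states that share.

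The items most directly tied to how a dose is injected are the injection-site items. Section 3.1.1.1 lists three of them (pain; pruritus; swelling, erythema and induration) among 18 solicited reactions, and all three would be affected.

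**Working it through.** **1. Does the text imply one CoronaVac group?** Set side by side:

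| SAP section | Grouping stated | Route named? |
|---|---|---|
| 4.3 safety populations | at least one dose, data reported | no |
| 6.1.1.1 solicited reactions | age category, vaccine type; tests between vaccines | no |
| 6.2.1 unsolicited events | none | no |
| 6.3 subgroups | age, health history | no |
| 5.1.1, 6.1.2.11, 6.1.2.12 immunogenicity | intradermal against intramuscular | yes |
| 6.2.2 efficacy prediction | vaccine, with route mentioned in addition | yes |

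Section 6.2.2 treats route as something apart from the vaccine, so vaccine type in 6.1.1.1 cannot be assumed to include it. A single CoronaVac group is therefore what the wording produces, although the SAP never states it.

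**2. The plan's own figure on adverse-reaction percentages.** Section 5.1.2 says 110 adolescents give ±7.5 points with 95% confidence at 80% prevalence. n = 0.80 × 0.20 × (1.960/0.075)² = 109.3, so 110. This reproduces and is not in dispute.

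**3. Effect of mixing routes.** Let w be the intradermal share of CoronaVac recipients, and p_IM, p_ID and p_B the reaction rates for intramuscular CoronaVac, intradermal CoronaVac and BNT162b2.

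- Mixed CoronaVac rate = (1 − w) × p_IM + w × p_ID
- Difference shown = (p_B − p_IM) − w × (p_ID − p_IM)

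The SAP gives none of these inputs; all the values below are assumptions.

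With p_IM = 30%, p_ID = 70%, p_B = 50% and w = 20%, the mixed rate is 0.8 × 30 + 0.2 × 70 = 38%. The difference shown is 50 − 38 = 12 points, against 50 − 30 = 20 for intramuscular alone.

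A second set has p_IM = 20% and p_B = 50%, an intramuscular difference of 30 points:

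| Share w | Difference shown, p_ID = 50% | Difference shown, p_ID = 80% |
|---|---|---|
| 10% | 27 points | 24 points |
| 25% | 22.5 points | 15 points |
| 50% | 15 points | 0 points |

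If p_ID equals p_IM, or w is close to zero, the distortion vanishes.

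**4. Precision after splitting by route.** Half-width = 1.960 × √(0.16/n) at 80% prevalence: n = 30 gives ±14.3 points, n = 60 gives ±10.1, n = 110 gives ±7.5 and n = 120 gives ±7.2.

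**The case against.** The strongest reply is that the SAP nowhere says the routes are combined. The descriptive immunogenicity sections (6.1.2.1 to 6.1.2.6) are equally silent on route, though the plan clearly separates routes for immunogenicity elsewhere. Arms B and C are used in 4.2 without definition, and section 2.2.2 is not in the text at hand, so intradermal recipients may belong to a separate arm. Section 5.1.2 sets a target of 120 for each vaccine regimen and age group directly after its precision statement on adverse reactions. If regimen includes route, that points towards separate reporting.

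Part of this stands. Combining the routes is implied, not stated, and the conclusion must be worded that way. It does not remove the point. For immunogenicity the silence of the descriptive sections is made good by explicit route contrasts; nothing does this for safety. Section 6.1.1.1 states its own grouping, and it does not use the term regimen. Nothing here rests on 2.2.2.

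Two stronger inferences are not supported. A reader might take the recruitment target to imply that half of the CoronaVac recipients are intradermal. That holds only if regimen includes route, which the SAP does not say. A reader might also assume that participants chose their route. Section 2.2.1 says they elect the vaccine; the SAP does not say how route was assigned.

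A further objection concerns the remedy. Formal intradermal-against-intramuscular tests for 18 reactions after each of two or three doses would add 18 × 2 = 36 to 18 × 3 = 54 tests per age group, in a plan that makes no allowance for multiplicity (5.1.3). This stands, and a descriptive split is enough.

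**Conclusion.** The plan should be changed. As written, it specifies no reactogenicity or adverse-event result by route, and its vaccine comparison would set BNT162b2 against a mixture of intramuscular and intradermal CoronaVac. This weakens the answer to primary objectives 1 and 2.

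The size of the effect cannot be determined from the SAP. The fall from 20 to 12 points, and the range in the second set of rates, are illustrations under assumed rates and shares. They show that the mixture can matter; they are not evidence that this trial's comparison is materially biased or that reaction rates differ by route. The conclusion rests on reading vaccine type in 6.1.1.1 as excluding route, which 6.2.2 supports, and on no arm definition outside this document that already separates the routes.

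**What to change.** - In 6.1.1.1 and 6.2.1, report BNT162b2, intramuscular CoronaVac and intradermal CoronaVac as separate groups within each age category, with n, N and Clopper-Pearson 95% intervals.
- Make the Fisher comparison between vaccines BNT162b2 against intramuscular CoronaVac.
- Show intradermal beside intramuscular CoronaVac in the same age group, descriptively and without added tests.
- Add route to the list in 6.3.

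Route must already be recorded, since 6.1.2.11 and 6.1.2.12 need it, so no new data are required. The work is a wording change and one more column or bar per display. The cost is a smaller N per CoronaVac column and correspondingly wider intervals, as computed above. That is acceptable for a descriptive safety result.
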